10.8 Medical History and Concurrent Diseases

Medical history with an end date prior to first dose of IMP in the first treatment period is considered as medical history, and those that are ongoing on and after first dose of IMP are considered as concurrent diseases.

10.9 Adverse Event Flags

Treatment emergent adverse event (TEAE) flags will be marked for adverse events if they occurred or worsened on or after the first administration of IMP in the first study period. Adverse events occurring during screening and first baseline period will not be considered as TEAEs.

If the events cannot be determined as TEAE due to partial dates, then the worst case will be considered and they will be flagged as TEAE in the respective study period based on AE start date.

Related Adverse Events will be flagged for Possibly, Probably and Definitely Related adverse events. Adverse events that started on or after first dose of IMP in treatment period 1 or during wash-out will be counted in the first treatment period and allocated to the treatment received in treatment period 1. AEs that commenced on or after first dose of IMP in treatment period 2 will be counted in the second treatment period and assigned to the treatment received in treatment period 2. If an adverse event occurred in first period and continued to second period, it will be counted in both study periods (as 'New' in period 1 and 'Ongoing' in period 2). If AEs have same month/year as IMP date, then the

decision regarding whether to consider them as 'Ongoing' or 'New' within the period will be decided in the blinded review meeting.

Suspected unexpected serious adverse events (SUSARs) will be flagged by the Sponsor and included in analyses datasets.

Programming note for adverse events:

- Period 1, Ongoing - if AE start date is prior to first dose of IMP in period 1 and end date is on or after first dose of IMP in period 1.
- Period 1, New - if AE start date is on or after first dose of IMP and before first IMP date in period 2.
- Period 2, Ongoing - AEs that were new or ongoing in period 1, with end date on or after first IMP date in period 2.
- Period 2, New - if AE start date is on or after first dose of IMP in period 2.

Adverse events will either be flagged in "Ongoing" or "New" within a study period, but not in both.

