12.2 Recording of adverse events

For Australian sites, all events from Screening to prior to the first dose of IMP will be captured as medical history. All events occurring during and following the first administration of IMP will be reported as Aes or SAEs (if criteria met) until the completion of the End of Study Evaluation visit.

In the UK, all SAEs will be recorded from the time of the subject signing an informed consent. All non serious Aes prior to the first dose of IMP will be captured as medical history. All events occurring during and following the first administration of IMP will be reported as Aes or SAEs (if criteria met) until the completion of the End of Study Evaluation visit.

AEs that are ongoing at the End of Study Evaluation visit will be followed up until the event has resolved or stabilised. All follow-up information will be recorded in the subject's source records. All spontaneously volunteered and enquired for, as well as observed AEs, will be recorded in the subject's source records as well as the CRF.

It is preferable that AEs and SAEs be reported as diagnoses if available, rather than individual signs and symptoms. SAEs should be reported and documented in accordance with the procedures in Section 12.4. The following data should be documented for each AE: the description of the event, start and stop dates, intensity, causality and outcome must be recorded, as well as any actions taken.

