11.7.1.1 Overall Adverse Events

The number and percentage of subjects and number of events will be summarized by treatment overall and within each study period for the following categories:

1. All adverse events reported
2. Treatment emergent adverse events (TEAEs)
3. Serious adverse events
4. Serious treatment-emergent adverse events
5. Related treatment-emergent adverse events
6. Related treatment-emergent serious adverse events
7. Suspected unexpected serious adverse events (SUSARs)

8. Treatment-emergent adverse events led to death
9. Treatment-emergent adverse events led to study discontinuation

In DDP: Table 14.3.1.1.1, Table 14.3.1.1.2

The summary by treatment overall will only include 'New' events within each treatment. All adverse events will be listed by subject, system organ class and preferred term sorted by event start dates.

In DDP: Listing 16.2.7.1 to 16.2.7.5

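### An adverse event that carries over the crossover on one record and then worsens is counted only under the first treatment in the overall adverse event summary by treatment

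*SAP*

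**What the plan says.** SAP 10.9 defines a treatment-emergent event as one that qualifies "if they occurred or worsened on or after the first administration of IMP in the first study period". The start of Period 2 is not used as a second reference point.

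The programming note in the same section then assigns flags:

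- 'New' in Period 1: "if AE start date is on or after first dose of IMP and before first IMP date in period 2", so washout is included.
- 'Ongoing' in Period 2: "AEs that were new or ongoing in period 1, with end date on or after first IMP date in period 2".
- 'New' in Period 2: "Period 2, New - if AE start date is on or after first dose of IMP in period 2".
- An event carries one flag or the other "within a study period, but not in both".

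Three summaries use these flags. For the overall table, SAP 11.7.1.1 says: "The summary by treatment overall will only include 'New' events within each treatment". SAP 11.7.1.2 (SOC and preferred term) includes both 'Ongoing' and 'New' events by treatment. SAP 11.7.1.3 (severity) states no inclusion rule.

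On data capture, Protocol 12.2 lists what is documented for each event: "the description of the event, start and stop dates, intensity, causality and outcome must be recorded". No date of worsening is listed. Protocol 12.4 treats a non-serious event that becomes serious as follow-up information to be reported.

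**The concern.** In a crossover, each subject's events have to be attributed to the treatment being taken. The SAP accepts that worsening matters, since it is part of the treatment-emergent definition, but the attribution rule does not use it. An event that is mild on the first treatment and becomes serious on the second keeps its original start date. It is therefore 'Ongoing' in Period 2 and cannot also be 'New' there.

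The overall table has rows for serious, related, SUSAR, fatal and discontinuation events, and it is the most compact comparison of the two treatments on safety, which is a secondary objective. An event that started on placebo and became serious, or led to withdrawal, only on LAT8881 would stand in that table under placebo. In the opposite sequence the error runs the other way.

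**Working it through.** The plan gives no figure on this point, so there is none to reproduce. The check applies the SAP 10.9 programming note literally to example events, with first doses on the nominal Days 1 and 50, and counts them under each inclusion rule.

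Rules, with s = start day and e = end day:

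- Period 1 'Ongoing' if s < 1 and e ≥ 1; 'New' if 1 ≤ s < 50.
- Period 2 'New' if s ≥ 50; 'Ongoing' if flagged in Period 1 and e ≥ 50.

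The day of worsening enters neither rule. Counts are shown as (first treatment, second treatment).

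| Event | Period 1 flag | Period 2 flag | 'New' only (11.7.1.1) | 'New' + 'Ongoing' (11.7.1.2) |
|---|---|---|---|---|
| A. Starts Day 20, worsens Day 60, ends Day 70; one record | New | Ongoing | (1, 0) | (1, 1) |
| B. Starts Day 35 in washout, worsens Day 60, ends Day 70; one record | New | Ongoing | (1, 0) | (1, 1) |
| C. As A, but first record closed Day 59 and worsening entered as a second record from Day 60 | New; none | Ongoing; New | (1, 1) | (1, 2) |

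Three results follow.

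1. In A and B the overall table gives the second treatment 0. An event that merely persisted from Day 20 to Day 70 at the same grade would give the same counts in both columns, so neither table can tell worsening from persistence.
2. In C the overall table is right. The outcome depends on how the site recorded the worsening, not on what happened to the subject.
3. In C the SOC/PT event count for the second treatment becomes 2 (the old record plus the new one), although it is one subject. Because the tables use different inclusion rules, their event counts by treatment need not reconcile.

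Size per event: the plan aims for 44 completers and 44/0.8 = 55 recruited. If the treatment columns hold between 44 and 55 subjects, one subject moves a row by 1/55 = 1.8% to 1/44 = 2.3%.

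**The case against.** The main objection concerns data capture. Asking for one intensity per event fits opening a new record at each grade change at least as well as keeping one record, and the eCRF guidance is not among the documents. This stands, so the point is conditional. Protocol 12.4 leans towards a single record for an event that becomes serious, but it does not settle the matter. A reader might take the 'worsened' wording and the 'Period 1, Ongoing' class as proof that single records were intended. They are not: the class mirrors the concomitant medication note in SAP 10.6, and the wording fits the protocol's own definition of worsening as an adverse event.

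Three stronger readings are also unsupported.

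- **The event disappears from all second-treatment output.** It does not. SAP 10.9 counts a carried-over event in both periods, the SOC/PT tables include it under both treatments, the 'New' restriction is stated only for the summary by treatment overall and not for the one within periods, and all events are listed.
- **The overall table shows the grade under the wrong treatment.** That table has no severity rows. Severity belongs to SAP 11.7.1.3, which states no 'New'-only rule.
- **Conditions present before Day 1 that later worsen are generally lost.** Protocol 12.2 captures pre-dose events as medical history, and Protocol 12.1.1 and 12.3 make a clinically significant worsening after dosing an event in its own right. Only serious events recorded before dosing at UK sites could be 'Ongoing' in both periods and so be missing from the overall table.

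Materiality is also limited. The event must last through the IMP-free Days 29 to 49, or start within them, and then worsen. Safety endpoints are summarised descriptively, so no hypothesis test depends on the count.

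**Conclusion.** The point holds for one output, the overall adverse event summary by treatment in SAP 11.7.1.1, and on one condition: that a worsening is kept on the original record. The stated rules then count an event from Period 1 or washout that worsens, becomes serious or leads to discontinuation during the second treatment under the first treatment only, (1, 0) where (1, 1) is right. The direction depends on sequence.

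Each affected subject moves a row by about 2 percentage points, assuming 44 to 55 subjects per treatment column. The number affected is unknown and may be small. The gap still deserves closing, because it falls on the rows where single events carry weight and the correction is short.

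**What to change.** In SAP 10.9, apply the occurred-or-worsened test separately against the first dose of each period. An event whose grade rises, or that becomes serious, from the first Period 2 dose onward is then 'New' for the Period 2 treatment. Say also under which treatment a discontinuation in Period 2 is counted when the event carried over without a change of grade.

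Instruct sites to enter such a worsening as a new event record with its own start date. State one inclusion rule across SAP 11.7.1.1 to 11.7.1.3, and say how a closed first record and its successor are counted, so that case C does not give two events in one table and one in another.

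The cost is minor reprogramming and a short addition to the eCRF guidance, with no extra visits or subjects. The limitation is retrospective: for subjects already treated whose records were not split, the date of worsening may not be recoverable. Such events should then be identified in the listings and described individually.

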12.3 Clinical lab abnormalities and other abnormal assessments

Abnormal laboratory findings (e.g., clinical chemistry, haematology, and urinalysis) or other abnormal assessments (e.g., ECG, vital signs) per se are not reported as AEs. However, those abnormal findings that are deemed clinically significant or are associated with signs and/or symptoms must be recorded as AEs (and recorded as an SAE if they meet the criteria of being serious) as described previously. Clinically significant abnormal laboratory or other abnormal findings that are present at baseline and worsen after first dose of IMP are to be considered AEs (and SAEs if serious).

The investigator should exercise his or her medical and scientific judgment in deciding whether an abnormal laboratory finding or other abnormal assessment is clinically significant. Usually, the abnormality should be associated with a clinically evident sign or symptom, or be likely to result in an evident sign or symptom in the near term, to be considered clinically significant. A clinically significant laboratory abnormality in the absence of clinical symptoms may jeopardize the subject and may require intervention to prevent immediate consequences.

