11.7 Safety Analyses

All safety summaries will be based on the Safety population. Screening visits will not be included in summaries, and will only be listed. Baseline measurements will be summarized under 'PreTreatment' for all safety summaries. EOS / Early Termination visits will be summarized in 'Total' within last treatment taken.

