11.7.3.4 Electrocardiogram Assessments

Number and percentage of subjects with overall findings (Normal, Abnormal Not CS and Abnormal CS) will be summarized by treatment overall and within each study period and visit. Percentages will be based on safety population.

In DDP: Table 14.3.6.1

ECG findings will be listed by treatment sequence, subject ID, treatment period and visit.

In DDP: Listing 16.2.9.3

12 Changes to Planned Analyses

- Mixed Effect Regression analyses for change from baseline in NPRS mean scores is combined for weeks 1-4 within the same model, instead of week 4 and weeks 1-3 separately as defined in study protocol.
- McNemar's test is included to compare proportion of subjects achieving $\geq 30\%$ and $\geq 50\%$ reduction in mean NPRS scores across study periods.
- Analysis of covariance is included to see the effect of treatment and placebo in maximum reduction from baseline adjusting for baseline NPRS mean scores and time taken to reach maximum reduction.
- Mixed Effect Regression analyses for change from baseline in NPRS mean scores including clinical diagnosis (PHN, DPN) and baseline [REDACTED] as additional covariates is

considered as secondary analyses instead of exploratory analyses since subgroups PHN and DPN were considered clinically relevant.

- PK Analyses is not included in this Statistical Analysis Plan, and will be done separately. PK Population is replaced with Per-Protocol population for subjects with NPRS assessments taken at timepoints in baseline and Week 4 visits.

13 Index of Tables, Listings and Graphs

Refer LAT-NP-001_Data Display Plan (Ver: 2.00) for the list of Tables, Listings and Graphs.

14 References

1. ICH. ICH Harmonized Tripartite Guideline: Statistical Principles for Clinical Trials E9. 1998.
2. ICH. ICH Harmonized Tripartite Guideline: Structure and Content of Clinical Study Reports E3. 1995.

15 Appendices

15.1 painDETECT questionnaire

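### The SAP adverse event rule never credits a finding first made pre-dose on Day 50 to the Period 1 treatment, and the ECG table shows pre-dose Day 50 ECGs under the Period 2 treatment

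*SAP*

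**What the plan says.** **Timing of the tests.** Protocol 2.2 and SAP 5.2 mark the Visit 5 ECG and safety laboratory samples as pre-dose. Vital signs are taken before the dose and half an hour after it. Protocol 8.6.1 allows dosing before the laboratory results are known.

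**What becomes an adverse event.** Under protocol 12.3, "those abnormal findings that are deemed clinically significant or are associated with signs and/or symptoms must be recorded as AEs". Protocol 12.2 says that "the description of the event, start and stop dates, intensity, causality and outcome must be recorded"; no clock time is on that list.

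**How an event is given to a period.** The SAP 10.9 programming note has two rules for new events. The rule for the first period closes at a calendar date: "Period 1, New - if AE start date is on or after first dose of IMP and before first IMP date in period 2". The rule for the second period is worded differently, because it opens at a dose and not at a date: "Period 2, New - if AE start date is on or after first dose of IMP in period 2".

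The narrative above the note says that "AEs that commenced on or after first dose of IMP in treatment period 2 will be counted in the second treatment period". It gives events that start in treatment period 1 or during wash-out to the Period 1 treatment. SAP 11.7.1.1 builds the overall summary by treatment from 'New' events only, so this flag decides the treatment column.

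**How ECGs are shown.** SAP 10.3 places Day 50, Visit 5 in Period 2, as analysis visit Visit 2/Visit 5. SAP 10.12.1 takes the safety baseline for both periods from before Day 1 dosing, and SAP 11.7 puts baseline values under a pre-treatment heading. SAP 11.7.3.4 says that ECG findings "will be summarized by treatment overall and within each study period and visit".

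**The concern.** Before the Period 2 dose, the only study drug a subject can have taken is the Period 1 treatment. An abnormality first seen in the Visit 5 pre-dose tests can therefore say something about that treatment, or about background, but nothing about the treatment that is about to start. A rule that credits it forward puts findings made after LAT8881 under placebo. It also puts findings in subjects who have never had LAT8881 under LAT8881.

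Safety and tolerability is a stated objective, and the adverse event tables by treatment are its main comparison. Those tables have no visit row in which a reader could spot such events.

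**Working it through.** The plan gives no figure on this point to reproduce. The check applies the SAP 10.9 rules to onset days around the second period, with first doses on Day 1 and Day 50, and then traces the ECG through the display rules.

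**Adverse event flags**

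| Onset | Flag from the programming note |
|---|---|
| Day 35 (washout) | Period 1, New |
| Day 45 (second baseline) | Period 1, New |
| Day 49, resolved that day | Period 1, New |
| Day 49, continuing to Day 55 | Period 1, New and Period 2, Ongoing |
| Day 50 before the dose, date only | Period 2, New |
| Day 50 after the dose, date only | Period 2, New |
| Day 50 before the dose, Period 2 rule read at clock time | no flag |

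The upper limit of 'Period 1, New' is a date, so a Day 50 onset can never meet it. The lower limit of 'Period 2, New' is a dose. With dates only, onsets before and after the dose look the same and both become Period 2. With times, the pre-dose onset falls between the two rules. Neither reading reaches the Period 1 treatment. A laboratory finding that is read and dated after Day 50 also becomes 'Period 2, New', although the sample was pre-dose.

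The narrative does not fill the gap. It assigns Period 2 only from the Period 2 dose, so it excludes a pre-dose event. Its Period 1 limb runs to the end of washout, which SAP 10.4 sets at Day 42. The note gives onsets through Day 49 to the Period 1 treatment, and reverses direction only on Day 50.

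**Direction of the effect in the 'New' table.** Take n subjects per sequence (equal sequences assumed). Let a be the mean number of these pre-dose Day 50 findings per subject after LAT8881, and p the mean number after placebo.
- Correct assignment: LAT8881 column n·a, placebo column n·p, so a contribution of n(a − p) to the difference.
- Date-only rule: LAT8881 column n·p, placebo column n·a, so a contribution of −n(a − p).
- Unflagged: a contribution of 0.

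If a > p, the date-only rule moves the difference in counts by −n(a − p) − n(a − p) = −2n(a − p). If nothing from Period 1 persists at Day 50, a = p and the difference in counts does not move, although individual events still stand in the wrong column. The documents give neither a nor p.

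The summary by system organ class and preferred term (SAP 11.7.1.2) counts 'New' and 'Ongoing' together. A reassigned event would be 'Period 1, New' and also 'Period 2, Ongoing', as a continuing Day 49 onset already is. In that table the present fault is that the event is missing from the Period 1 treatment.

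**ECG table**
1. The Visit 2 ECG, when it is the baseline, goes under the pre-treatment heading (SAP 10.12.1, 11.7).
2. The Visit 5 ECG is not a baseline, so it stays in Period 2 (SAP 10.3, 10.4).
3. The Visit 2/Visit 5 row in the treatment columns is therefore in effect the Day 50 pre-dose ECG.
4. In that row, the placebo column holds LAT8881-then-placebo subjects, whose only exposure is LAT8881. The LAT8881 column holds placebo-then-LAT8881 subjects, who have had no LAT8881.

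**The case against.** **The misassignment is inferred.** The narrative and the 'Period 2, New' rule refer to the dose; only one limit refers to a date. The eCRF may hold onset times, which protocol 12.2 does not exclude. This stands as a limit on the claim: with times, the event is unclassified rather than misassigned. Either way the rule needs repair.

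**Blinded review.** SAP 10.9 leaves events in the same month and year as the dosing date to that meeting. The sentence may be aimed at partial dates, and it decides only 'Ongoing' against 'New' within a period. It could keep an event out of the Period 2 'New' count, but it does not credit the Period 1 treatment.

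**Few events are exposed.** Symptoms with an earlier onset date, and abnormalities already recorded on Day 28, go to Period 1. What remains is a clinically significant finding first identified in the Visit 5 pre-dose assessment, about three weeks off drug. Adverse events are also listed by subject with start dates, so cases can be traced. This stands, and it limits the size.

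**The ECG row is a matter of display.** The row carries its visit name, the assessment schedule marks the ECG as pre-dose, and the Data Display Plan was not available. A careful reader could work it out, but nothing in SAP 11.7.3.4 says so.

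**Stronger readings that a reader might infer.** One is that ECG and laboratory differences between treatments shrink by a calculable amount, because one of three scheduled ECGs after Day 1 (Days 28, 50, 77) and one of four laboratory sets (Days 28, 50, 77, 91) is the Day 50 pre-dose one. The documents do not support this: those summaries are by visit, no difference pooled over visits is planned, and no abnormality rates are given. Another is that the Day 91 rule, "EOS / Early Termination visits will be summarized in 'Total' within last treatment taken", shows the SAP contradicting itself. That comparison is weak, because no treatment follows Day 91 and no other assignment is possible. The real conflicts are between the 10.9 narrative and its note, and between Day 50 pre-dose and Days 29 to 49.

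**Conclusion.** The point holds in a limited form. The SAP 10.9 programming note cannot assign a finding first made pre-dose on Day 50 to the treatment the subject has actually taken. It credits the finding to the next treatment if only dates are held, and leaves it unflagged if times are held. The ECG table shows pre-dose Day 50 readings under the Period 2 treatment without saying so.

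The number of adverse events affected cannot be computed from the documents and is probably small. Any date-only misassignment runs in both sequences. It would tend to dilute a treatment difference in adverse event counts if effects of the Period 1 treatment are still visible at Day 50, which is uncertain after three weeks off drug. The conclusion assumes that adverse event timing is held as listed in protocol 12.2, and that the tables follow the SAP text.

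**What to change.** In SAP 10.9, reconcile the narrative and the programming note:
- Assign to the Period 1 treatment any adverse event identified from a Visit 5 pre-dose assessment, or with onset before the Period 2 dose on that day. Use the pre-dose label of the assessment or a before/after-dose flag. Tying the rule to the assessment also catches laboratory findings dated later.
- Keep 'Period 2, New' for onsets after the dose.
- Extend the narrative's Period 1 limb beyond washout, up to the Period 2 dose.

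In SAP 10.3, 11.7 and 11.7.3.4, show the Visit 5 ECG as a labelled pre-dose, off-drug value following the Period 1 treatment, not as an on-treatment Period 2 result. The laboratory tables use the same visit mapping, and the same label would serve there.

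The cost is SAP wording and a few lines of programming before database lock. Events found by a scheduled pre-dose test need no new data. The small downside is that a symptom with a Day 50 onset and no recorded time needs a site query or a decision at the blinded review.
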